- Modify the inclusion criteria related to coagulation parameters, neutrophil parameters, the use of the previous MF treatment, clarify the weight loss decrease timeframe:
- Coagulation parameters: INR and PTT increased from 1.2 x ULN to 1.5 x ULN based on the observation that eligible patients may have slightly elevated coagulation parameters as per information from the recently completed Phase III [INCB 1824-351] study and because bleeding risks are low below this threshold.

- Deletion of the fibrinogen and D-dimer or fibrinogen degradation products (FDP) criteria no longer required to qualify a patient in the study. There is no clear evidence that these particular cut-off values correlate with the risk of bleeding.
- Neutrophil parameters: ANC allowed value decreased to  $1 \times 10^9/L$  at Screening as per other INC424 studies.
- Discontinuation of prior MF therapy decreased to 7 days prior to Screening evaluations in order not to leave the patients without treatment for a long period of time.
- Weight loss decrease timeframe defined within the past year in order to ensure that the constitutional symptom is relevant within the study timeframe.
- Modify the exclusion criteria related to PLT transfusion exclusionary period, clarify the frequency of the use of drugs that interfere with coagulation or inhibit PLT function, clarify the bilirubin parameter check, clarify the stem cell transplantation option, delete the ulcerative diseases as a gastrointestinal function impairment, replace the word coagulopathy by bleeding diathesis and addition of an exclusion criterion related to the patient life expectancy:
- PLT transfusion exclusionary period decreased to 14 days prior to Screening evaluations, in order to palliate any urgent needs and since the half-life of a platelet transfusion is approximately one week.
- Only regular use of drugs that interfere with coagulation or inhibit PLT function are prohibited in the study. The investigator will assess the regularity of use of such agents versus occasional use. Selective COX-2 inhibitors and acetaminophen deleted from the list of prohibited medication as these drugs do not affect coagulation or platelet functions. Clarify that low dose aspirin ( $\leq 125$  mg/day) is allowed. Clarify that medications used for myelofibrosis are prohibited during the treatment period but are allowed during the 30-day follow-up period after the End of Treatment.

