### 3 Investigational plan

#### 3.1 Study design

This is a Phase Ib, open-label, dose-finding study of the JAK inhibitor INC424 tablets administered orally to patients with Primary Myelofibrosis (PMF), Post-Polycythemia Vera-Myelofibrosis (PPV-MF) or Post-Essential Thrombocythemia-Myelofibrosis (PET-MF) and baseline platelet counts  $\geq 50 \times 10^9/L$  and  $<100 \times 10^9/L$ .

The study will consist of 2 periods:

- The core study period [first 168 days of study]
- The extension study period [beyond Week 24 (168 days) to 3 years].

The core study includes patients in one of two phases (Figure 3-1), (a) a dose escalation phase and (b) a safety expansion phase.

In the dose escalation phase, successive cohorts of newly enrolled patients will receive increasing doses of INC424 until the MSSD is determined. The MSSD will be the dose level most closely associated with a posterior DLT probability of between 16% and 33% that does not also have a greater than 25% probability of excessive toxicity. In the safety expansion phase, 20 patients in total (10 patients from each stratum), additional to those treated at the MSSD during dose escalation, will be treated at the respective MSSD for their stratum.

The treatment period for an individual patient is 3 years [except in the UK, which is up to LPFV + 156 weeks]: it will begin on Study Day 1 and will continue until the patient completes the study or is permanently discontinued.

The approximate number of patients planned to be enrolled in the Dose-Determining Set (DDS) for this study is 72, assuming 3 patients are treated at each dose level and 5 dose levels are tested in both strata, and including the additional patients to be enrolled into the 10 mg BID dose which is to be evaluated as a starting dose.

DLT will be defined as the occurrence of any of the following **treatment-related** toxicities occurring through Study Day 28:

- any grade  $\geq 2$  hemorrhagic event
- any grade thrombocytopenia requiring PLT transfusion
- PLT counts  $< 25 \times 10^9/L^*$
- grade 4 neutropenia (ANC  $< 0.5 \times 10^9/L$ )\*

- grade  $\geq$  3 febrile neutropenia\*
- grade  $\geq$  2 total serum bilirubin with coincident direct bilirubin  $\geq$  0.5 mg/dL
- grade 3 non-hematologic toxicity for  $\geq$  7 consecutive days
- grade 4 non-hematologic toxicity

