### **5.1.10 Prohibited concomitant therapy**

The following medications are prohibited during the study:

- Any prior or concomitant use of another JAK inhibitor.
- Any investigational medication (other than INC424) that is not approved for any indication. Use of such medications within 30 days or 5 half-lives, whichever is longer, prior to the first dose of study drug and during the study through the Safety Follow-up Visit is prohibited.
- Use of the potent inducers of CYP3A4 (such as rifampin and St John's Wort), is not permitted at any time during participation in the study (see [Appendix 7](#) for a list of CYP3A4 inducers).
- Any regular use of drugs that interfere with coagulation or inhibit PLT function (except low doses aspirin  $\leq$  125 mg/day which are allowed) and non-steroidal anti-inflammatory drugs (NSAIDs). For a complete list, see [Appendix 4](#).
- Any other medication for myelofibrosis during the treatment period: hydroxyurea, busulfan, interferon, lenalidomide, thalidomide, anagrelide.

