- There is disease progression (see [Section 6.2.1](#)). As an exception, if, despite disease progression which is documented by  $> 40\%$  increase in spleen size and not by leukemic transformation, the Investigator believes that it is in the patient's best interest to continue therapy with INC424 due to symptomatic improvement, the patient may continue therapy, only after consultation with the Sponsors.
- Use of prohibited treatments (refer to Appendix 1) as determined by Novartis
- Patient undergoes splenic irradiation
- Patient undergoes splenectomy. As an exception, patients who participate in the safety expansion phase of the study are allowed to continue in the study, provided that they have fully recovered from the surgery and are discharged from the hospital.
- Death

- Any other protocol deviation that results in a significant risk to the patient's safety
- Patient has completed 3 years of treatment and another treatment option is available
- Patient is non-compliant with the protocol
- Study is terminated by the Sponsor

Patients whose treatment is interrupted or permanently discontinued from the study due to an Adverse Event or abnormal laboratory value must be followed at least once a week for 30 days, and subsequently at 4-week intervals, until resolution or stabilization of the event, whichever comes first. All patients will be followed for Adverse Events and Serious Adverse Events for 30 days following the last dose of INC424.

Patients who discontinue study treatment and study participation should return for the assessments indicated in [Table 6-1](#), [Table 6-2](#), and [Table 6-3](#) for safety reasons. If they fail to return for these assessments for unknown reasons, every effort (e.g. telephone, email, letter) should be made to contact them as specified in [Section 6.1.6](#).

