2.3 Safety evaluation

For all safety analyses, the Safety Set will be used, except for summaries of DLTs, which will be presented for the DDS. All listings will be presented by dose levels and all tables will be presented by groups of dose levels in the Safety Set.

The overall observation period will be divided into three mutually exclusive segments:

1. pre-treatment period: from day of patient's informed consent to the day before first dose of study medication
2. on-treatment period: from day of first dose of study medication to 30 days after last dose of study medication
3. post-treatment period: starting at day 31 after last dose of study medication.

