2.3.3 Laboratory abnormalities

For laboratory tests covered by the Common Terminology Criteria for Adverse Events (CTCAE) version 4.03 ([NCI 2009](#)). A grade 0 will be assigned for all non-missing values not graded as 1 or higher. Grade 5 will not be used. All lab values occurring between the treatment start date and 30 days after the end of the study treatment will be taken into account.

The following by-strata summaries will be generated separately for hematology, coagulation and biochemistry laboratory tests:

- frequency table for newly occurring or worsened on-treatment abnormalities
- shift tables using CTCAE grades to compare baseline to the worst on-treatment value

- for laboratory tests where CTCAE grades are not defined, shift tables using the low/normal/high/(low and high) classification to compare baseline to the worst on-treatment value.
- listing of all laboratory data with values flagged to show the corresponding CTCAE grades and the classifications relative to the laboratory normal ranges.

A summary and a plot will be produced for hemoglobin level and platelet count over time by visit and stratum.

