2.4.1 Pharmacokinetic-Pharmacodynamic data analysis

Relationships between the pharmacokinetic model predicted concentration/PK parameters and PD and safety/efficacy parameters were planned. All these as well as cytokines (if analysis

permitted) and depending on the quality of data available, may be reported in the a separate report Efficacy evaluation

Efficacy is a secondary endpoint in this study.

Change in spleen length below left costal margin

Spleen measurements by palpation will be obtained with a primary emphasis on the change in measurements from baseline to Week 24. Descriptive statistics will be provided for the spleen length and percent change from baseline over time. The percentage of patients with at least a 50% reduction in spleen length at any time point prior to cut off date (including both core and extension phases) as well as at least a 50% reduction in spleen length at Week 24 will be summarized with 95% confidence intervals.

Data will be summarized for the set of patients from the FAS who have a valid corresponding baseline assessment.

The percentage change in spleen length is defined as:

[figure not shown]
% Change = $(\text{Post-baseline spleen length} - \text{Baseline spleen length}) \times 100 / \text{Baseline spleen length}$.

A waterfall plot will be produced for best response in spleen length by stratum. Best response is defined as the minimum value in non-missing percent change from baseline.

Spleen length measurement with absolute and percent change from baseline will be summarized by time and by stratum.

For Interim Analysis, the current protocol time windows as specified in the latest protocol amendment Tables 6-3, 6-4, 6-5, 6-6 will be used for all visit based assessments.

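### The any-time and best spleen response have no cut-off at the start of another myelofibrosis drug, so a reduction obtained on the next drug can be credited to INC424

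*Protocol*

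**What the plan says.** **When other drugs are allowed.** Protocol Section 5.1.10 prohibits "Any other medication for myelofibrosis during the treatment period: hydroxyurea, busulfan, interferon, lenalidomide, thalidomide, anagrelide". Section 3.1 defines the treatment period: "it will begin on Study Day 1 and will continue until the patient completes the study or is permanently discontinued". The Amendment 1 rationale spells out the consequence: "medications used for myelofibrosis are prohibited during the treatment period but are allowed during the 30-day follow-up period after the End of Treatment". That sentence comes from an amendment log, but it matches the current text.

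**What is measured after the last dose.** Table 6-2 places spleen palpation, and Table 6-3 hematology, at the follow-up visit 30 days after the last dose. Under Section 6.1.4, patients whose treatment is interrupted or stopped for an adverse event or abnormal laboratory value "must be followed at least once a week for 30 days".

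**How the SAP uses those values.**
- Spleen (efficacy text following Section 2.4.1): a reduction of at least 50% counts "at any time point prior to cut off date (including both core and extension phases". Best response, shown in the waterfall plot, is the lowest non-missing percent change from baseline.
- Safety periods (Section 2.3): "on-treatment period: from day of first dose of study medication to 30 days after last dose of study medication".
- Laboratory (Section 2.3.3): "All lab values occurring between the treatment start date and 30 days after the end of the study treatment will be taken into account". The outputs include newly occurring or worsened abnormalities and "shift tables using CTCAE grades to compare baseline to the worst on-treatment value".

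None of these rules mentions the start of another myelofibrosis drug.

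**The concern.** Any-time response and best response are extremes over all available values. One favorable late palpation is enough to make a patient a responder, and no later value can undo it. If that palpation follows the start of another drug, the result is attributed to the patient's stratum and INC424 starting dose. The error can only push the response rate upward.

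Worst-grade laboratory tables work the same way in the other direction: a count lowered by the next drug can become the patient's worst value, and these tables carry no causality judgement.

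The stake is modest but real. Amendment 4 moved the Stratum 1 expansion to 10 mg BID because of dose reductions after the first cycle and clinical benefit seen across starting doses. Descriptive secondary summaries of this kind feed that sort of judgement, and the groups are small.

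**Working it through.** There is no sample size, power or error rate to reproduce here. The check compares the windows and then sizes the effect of one patient.

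**1. Can another drug and a spleen measurement coincide?** Yes. The ban in Section 5.1.10 ends with treatment, whereas the same section extends the ban on unapproved investigational drugs through the Safety Follow-up Visit. Section 5.1.6 expects symptoms to return on stopping and allows other medications to manage events after discontinuation. The follow-up palpation comes about 30 days later.

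**2. Does any rule exclude that measurement?** No. The any-time rule ends only at the data cut-off, and best response has no window. Nothing limits either to the on-treatment period, so even a palpation after day 30 could count.

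**3. Which follow-up visits fall in the laboratory window?**
- Table 6-2 (±3 days): permitted days 27 to 33, of which 27 to 30 are inside, so 4 of 7.
- Table 6-3 (+3 days): permitted days 30 to 33, of which only day 30 is inside, so 1 of 4.

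The nominal day-30 visit is inside under both.

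**4. What does one patient move?** The shift is 1/n. Counts come from the Amendment 4 rationale.
- Stratum 1: 24 + 3 = 27; 1/27 = 3.7 points.
- Stratum 2: 15 + 4 + 2 enrolled later = 21; 1/21 = 4.8 points.
- Stratum 1, 10 mg BID, target about 20: 1/20 = 5.0 points.

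The stratum shifts shrink if enrollment completes.
- Stratum 2 needs 10 − 6 = 4 more expansion patients: 21 + 4 = 25; 1/25 = 4.0 points.
- In Stratum 1, 24 − 9 = 15 escalation patients started below 15 mg BID, over four levels. With at least 3 per level, 3 to 6 of them started at 10 mg BID, so 14 to 17 more are needed. The stratum would reach 41 to 44, and one patient moves 2.4 to 2.3 points.

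**5. How does that compare with the precision?** The documents give no response rate, so these are assumptions with n = 20 and exact (Clopper-Pearson) 95% intervals.

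| Assumed responders | Rate (95% CI) | With one added |
|---|---|---|
| 6/20 | 30% (11.9–54.3) | 35% (15.4–59.2) |
| 8/20 | 40% (19.1–63.9) | 45% (23.1–68.5) |
| 10/20 | 50% (27.2–72.8) | 55% (31.5–76.9) |

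One patient shifts the estimate well within its interval.

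**6. What is untouched?** A DLT must be treatment-related and occur through Study Day 28. Week 24 response is reached only if a follow-up palpation happens to land there, that is, after a last dose around day 168 − 30 = 138.

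**7. Are the start dates available?** Table 6-2 lists later myelofibrosis therapy at the follow-up visit as database data, and Section 6.1.5 directs follow-up data to the Adverse Events and Concomitant Medications eCRFs. The SAP document history says presentation of antineoplastic medication was removed because it was not collected on the CRF. SAP Section 2.2.3 flags only concomitant records later than 30 days after treatment, so a drug started within the 30 days is listed without a flag.

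**The case against.** The strongest reply is that little is likely to happen. Protocol Section 1.1 says the older drugs all have limited effect on splenomegaly. A false responder must have missed 50% on INC424 and then reached it against baseline soon after switching. Another JAK inhibitor is prohibited during the study, and Section 3.8 expects completers to have continued access to INC424. This stands, and it keeps the point small.

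For laboratory data, the prespecified 30-day window is defensible. A reader might infer from the 3 to 5 hour half-life that INC424 effects are gone within two days and that the main tables should be cut at the switch. Plasma clearance does not show marrow recovery. Such a cut could remove true INC424 cytopenias and would give laboratory and adverse event tables different windows.

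Four other stronger readings are not supported:
- **That the 30 days are defined as on-treatment for spleen response.** The spleen rule does not use that period; its window is open.
- **That effects of the next drug are being credited to INC424.** The documents show only that they can be; no number of switchers is given.
- **That one patient moves a reported figure by 8.3 points (1/12, Stratum 1 patients starting at 15 mg BID).** SAP Section 2.3.3 and the waterfall plot report by stratum. Where the general grouping of Sections 2.1.1 and 2.3 applies, Group 3 pools 10/15 mg with 15/15 mg. With at least 12 + 3 = 15 patients, the shift is at most 6.7 points.
- **That stopping for an adverse event yields four or five blood counts or palpations.** Section 6.1.4 requires weekly follow-up of the event without specifying those assessments.

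Listings of laboratory data and concomitant medication would also allow patient-level checking, provided the new drug was recorded.

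**Conclusion.** The gap is real in the current text: nothing prevents a spleen value obtained on another myelofibrosis drug from counting toward any-time or best response. This is a minor point about descriptive secondary summaries. At the counts above, each affected patient is worth 3.7 points in Stratum 1, 4.8 in Stratum 2 and about 5 in the Stratum 1 10 mg BID group, with smaller stratum figures if enrollment completes. The number affected is unknown and probably small. The primary DLT endpoint and Week 24 response are essentially unaffected.

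The laboratory part is weaker: the 30-day window is a reasonable conservative choice, and what is missing is a way to see post-switch values separately. The conclusion assumes that the SAP text is complete on these rules and that some patients start another drug before their last palpation.

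**What to change.** 1. **Spleen.** In the SAP efficacy section, exclude values on or after the start of another myelofibrosis medication from the any-time response, best response and waterfall plot. List them with a flag. State which medications count, including how commercially supplied ruxolitinib is handled.
2. **Laboratory.** Keep the 30-day laboratory and adverse event windows. Flag post-switch laboratory values in the listing and add a supplementary worst-grade table cut at the start of the new drug.
3. **Dates.** Take start dates from the Concomitant Medications eCRF, and reconcile Table 6-2 with the statement in the SAP document history that antineoplastic medication was not collected on the CRF. If the dates are missing, report the limitation.

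The cost is a few SAP sentences, a date comparison and one extra table, subject to the dates being available. The any-time response rate may come out slightly lower. Adverse event reporting and patient care do not change.

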### Study status

Three patients have screen failed in the study, but no patient has started the treatment.

### Changes to the protocol

Changes to specific sections of the protocol are shown in the track changes version of the protocol using strike through red font for deletions and red underlined for insertions.

The following sections have been changed:

- Section 3.1, 3.1.3, 3.8, 3.9, 5.1.2.7, 6.1, 6.1.3, 6.1.4, 6.1.4.1, 6.1.4.2, 6.1.5, 6.2.1, 6.2.2.7.1, [REDACTED], 6.2.4.3, 8.4, 9, [REDACTED] 9.7, Table 6-1 and 6-2: extension of the study.
- Section 4.1 (inclusion criterion 6), 6.1.1, 6.1.1.1, 6.1.1.3, 9.2, 9.5.1, [REDACTED] definition of the baseline PLT count which will qualify the patient for the study.
- Section 4.1 (inclusion criteria 3, 6, 7 and 10): inclusion criteria related to the coagulation parameters, the neutrophil parameters, the use of the previous MF treatment.
- Section 4.2 (exclusion criteria 4, 6, 7, 8, 12, 13 and 22, and Section 5.1.10): exclusion criteria related to PLT transfusion exclusionary period, clarify the bleeding history timeframe, the frequency of the use of drugs that interferes with coagulation or inhibits the PLT function, the bilirubin parameter check, the stem cell transplantation option and addition of an exclusion criterion related to the patient life expectancy.
- Section 6.1.4.1. & 6.2.1: increase spleen size percentage has been changed to meet criteria for progression.
- [REDACTED]
- Section 5.2.3: clarification regarding the study drug label.
- 6.2.4.1.3: deletion of redundant information.
- 3.1, 9.8 and Appendix 13: approximate number of patients to enroll.

- 6.1.3 and 6.2.2.5: Laboratory-only visits.
- Table 5-5: dose escalation guidelines following thrombocytopenia different than grade 4 events.

### **IRB/IEC**

A copy of this amended protocol will be sent to the Institutional Review Boards (IRBs)/Independent Ethics Committees (IECs) and Health Authorities.

The changes described in this amended protocol require IRB/IEC approval prior to implementation. In addition, if the changes herein affect the Informed Consent, sites are required to update and submit for approval a revised Informed Consent that takes into account the changes described in this amended protocol.

## 1 Background

### 1.1 Overview of myelofibrosis and current treatment options

The four classic myeloproliferative neoplasms (MPNs) include chronic myelogenous leukemia (CML), polycythemia vera (PV), essential thrombocythemia (ET) and primary myelofibrosis (PMF). Myelofibrosis (MF) can present as a de novo disorder (PMF) or evolve secondarily from previous PV or ET (post-PV-MF or post ET-MF). Regardless of whether MF is a primary or secondary disorder, it is characterized by a clonal stem cell proliferation associated with production of elevated serum levels of multiple inflammatory and proangiogenic cytokines, a characteristic bone marrow stromal pattern that includes varying degrees of collagen fibrosis, osteosclerosis and angiogenesis and a peripheral blood smear showing a leukoerythroblastic pattern with varying degrees of circulating progenitor cells. Clinically, MF is characterized by progressive anemia, leukopenia or leukocytosis, thrombocytopenia or thrombocythemia and multi-organ extramedullary hematopoiesis most prominently involving the liver and spleen. Patients may experience severe constitutional symptoms, sequelae of massive splenomegaly (pain, limitations of movement, early satiety and shortness of breath, hepatic obstruction, and splenic infarction), a hypermetabolic state with cachexia, progressive hematopoietic failure, progression to leukemia, and premature death.

The median age at diagnosis is approximately 60 to 65 years. The incidence of PMF has been estimated at 1.5 cases per 100,000 people. Survival in MF varies with the presence or absence of specific risk factors. ([Cervantes et al 2009](#)) have recently published a multi-center analysis of risk factors and their impact on prognosis in patients with MF. They identified age of greater than 65 years, presence of constitutional symptoms (weight loss > 10% of the baseline value in the year preceding PMF diagnosis, unexplained fever, or excessive night sweats persisting for more than 1 month), anemia (Hgb less than 10 g/dL), leukocytosis (white blood cell count (WBC) greater than  $25 \times 10^9/L$ ), and a circulating blast percentage of 1% or higher as individually predictive of outcome. They demonstrated that patients could be distinctly grouped into four categories without overlapping median survival curves based upon their number of risk factors ([Table 1-1](#)).

